10.1.2.2. Laboratory data

Missing laboratory results (including immunological data) will not be replaced.

10.1.2.3. Daily recording of solicited events**10.1.2.3.1. Studies with electronic diaries**

For studies using electronic diaries for the collection of solicited adverse events, a solicited adverse event will be considered present only when a daily recording of grade 1 or more is present.

CONFIDENTIAL209544 (RSV MAT-004)
Statistical Analysis Plan Amendment 3**10.1.2.4. Unsolicited adverse events**

Unsolicited adverse event summaries are including serious adverse events unless specified otherwise.

Missing severity, relationship with study vaccine, and outcome of unsolicited adverse events will not be replaced and will appear as 'UNKNOWN' in all statistical output.

10.1.3. Data derivation**10.1.3.1. Age at vaccination in years**

When age at vaccination is to be displayed in years, it will be calculated as the number of complete calendar years between the date of birth and the date of vaccination. For example:

DOB = 10SEP1983, Date of vaccination = 09SEP2018 -> Age = 34 years

DOB = 10SEP1983, Date of vaccination = 10SEP2018 -> Age = 35 years

10.1.3.2. Weight

Weight will be presented in kilograms. Weights reported in pounds will be converted as follows:

Weight in kilograms = Weight in pounds / 2.2

10.1.3.3. Height

Height will be presented in centimeters. Heights reported in feet and inches will be converted as follows:

Height in centimeters = Height in inches x 2.54

10.1.3.4. Body mass index (BMI)

BMI will be calculated as follows:

$BMI = (\text{Weight in kilograms}) / (\text{Height in meters})^2$

10.1.3.5. Temperature

Temperatures will be presented in degrees Celsius (°C). Temperatures reported in degrees Fahrenheit (°F) will be converted as follows:

Temperature (Celsius) = ((Temperature (Fahrenheit) - 32) x 5)/9

CONFIDENTIAL209544 (RSV MAT-004)
Statistical Analysis Plan Amendment 3**10.1.3.6. Numerical serology results**

Numerical serology results will be derived from the content of IS.ISORRES in the SDTM dataset. For assays with a specific cut-off, the following derivation rules apply:

IS.ISORRES	Derived value
“NEG”, “-“, or “(-)”	cut-off/2
“POS”, “+”, or “(+)”	cut-off
“< value” and value is <= assay cut-off	cut-off/2
“< value” and value is > assay cut-off	value
“> value” and value is < assay cut-off	cut-off/2
“> value” and value is >= assay cut-off	value
“value” and value is < cut-off	cut-off/2
“value” and value is >= cut-off	value
All other cases	missing

10.1.3.7. Geometric mean titres (GMTs) and concentrations (GMCs)

Geometric Mean Titre (GMT) or Concentration (GMC) calculations are performed by taking the inverse logarithm of the mean of the log titre or concentration transformations. Antibody titres or concentrations below the cut-off of the assay will be given an arbitrary value of half the cut-off of the assay for the purpose of GMT/GMC calculation. The cut-off value is defined by the laboratory before the analysis and is described in the protocol.

10.1.3.8. Onset day

The onset day for an event (e.g. AE, medication, vaccination) is the number of days between the last study vaccination and the start date of the event. This is 1 for an event occurring on the same day as a vaccination (and reported as starting after vaccination).

10.1.3.9. Duration of events

The duration of an event with a start and end date will be the number of days between the start and end dates plus one day, i.e. an event that starts on 03MAR2018 and ends on 12MAR2018 has a duration of 10 days.

The duration of solicited events will be calculated as the sum of the individual days with the adverse event reported at grade 1 or higher during the solicited adverse event period.

10.1.3.10. Counting rules for combining solicited and unsolicited adverse events

For output combining solicited and unsolicited adverse events, all serious adverse events will be considered general events since the administration site flag is not included in the expedited adverse event CRF pages.

Multiple events with the same preferred term which start on the same day are counted as only one occurrence.

CONFIDENTIAL209544 (RSV MAT-004)
Statistical Analysis Plan Amendment 3**10.1.3.11. Counting rules for occurrences of solicited adverse events**

When the occurrences of solicited adverse events are summarized, each event recorded as having occurred during a specific period will be counted as only one occurrence regardless of the number of days on which it occurs. Also, in the case of co-administered study vaccines, an injection site reaction recorded for a subject following multiple vaccines will be counted as only one occurrence.

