Safety analyses in **infant subjects** will include summaries by study group and gestational age at birth (> 37 weeks or ≤ 37 weeks) of neonatal AESIs, MAEs, SAEs, AEs leading to study withdrawal, and the occurrence of RSV-associated RTIs, LRTIs, severe LRTIs, very severe LRTIs and RSV-associated hospitalizations.

All safety analyses will be performed on the Solicited Safety or Exposed sets.

	Primary Safety Endpoints	Statistical Analysis Methods
Maternal subjects	Occurrence of Solicited administration site and systemic events that occur during a 7-day follow-up period after vaccination (i.e. the day of vaccination and 6 subsequent days).	
The number and percentage with exact 95% CI of maternal subjects reporting each Solicited administration site event (any grade, each grade,) and solicited systemic event (any, each grade) during the 7-day (days 1 to 7) follow-up period after vaccination will be tabulated by maximum intensity per subject for each study vaccine group.
 
For fever during the 7-day follow-up period after vaccination, the number and percentage of maternal subjects reporting any fever (i.e., temperature ≥ 38 °C) and fever by half degree (°C) cumulative increments, any Grade 3 fevers, will be reported. In addition, the prevalence of any and Grade 3 fever will be presented graphically over time after vaccination.
 
The number and percentage of maternal subjects with at least one administration site AE (solicited and unsolicited), with at least one systemic AE (solicited and unsolicited) and with any AE during the 7-day follow-up period after vaccination will be tabulated with exact 95% confidence interval (CI) by group. The same computations will be done for Grade 3 solicited and unsolicited AEs, for any AEs considered related to vaccination, for any Grade 3 AEs considered related to vaccination and for any AEs resulting in a medically attended visit (i.e., MAEs).

	Occurrence of any protocol-specified hematological or biochemical laboratory abnormality at baseline (up to 15 days before vaccination) and Day 8 (Visit 2)	The number and percentage of subjects with hematology and biochemistry results outside central laboratory normal ranges will be tabulated to show Day 8 versus baseline. The maximum grading as described in [Sheffield, 2013] and in the SPM from Screening up to Day 8 will also be tabulated.

CONFIDENTIAL209544 (RSV MAT-004)
Statistical Analysis Plan Amendment 3

	Primary Safety Endpoints	Statistical Analysis Methods

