	Occurrence of unsolicited AEs that occur during a 30-day follow-up period after vaccination (i.e. the day of vaccination and 29 subsequent days).	
The number and percentage of maternal subjects with unsolicited symptoms within 30 days after vaccination with exact 95% CIs will be tabulated by group and by Medical Dictionary for Regulatory Activities (MedDRA) preferred term.
 
Similar tabulations will be done for Grade 3 unsolicited symptoms, for any causally related unsolicited symptoms, for Grade 3 related unsolicited symptoms and for MAEs.
 
The number and percentage of maternal subjects with at least one administration site AE (solicited and unsolicited), with at least one systemic AE (solicited and unsolicited) and with any AE during the 30-day follow-up period after vaccination will be tabulated with exact 95% confidence interval (CI) by group. The same computations will be done for Grade 3 solicited and unsolicited AEs, for any AEs considered related to vaccination, for any Grade 3 AEs considered related to vaccination and for MAEs.

	Occurrence of serious adverse events (SAEs), AEs leading to study withdrawal, and medically attended AEs from Visit 1 (Day 1) up to 6 weeks after delivery (Day 43 post-delivery, Visit 6).	
The number and percentage of maternal subjects with
 
 - at least one SAE; - at least one MAE from Visit 1 (Day 1) up to 6 weeks after delivery with exact 95% CIs will be tabulated by group and by Medical Dictionary for Regulatory Activities (MedDRA) preferred term. 
By-subject listings of SAEs, AEs leading to study withdrawal, and MAEs will be prepared (but will not be released until the final, unblinded analysis has been completed).

	Pregnancy outcomes from Day 1 (Visit 1) up to 6 weeks after delivery (Day 43 post-delivery, Visit 6). Outcomes are listed in Section 2.	
The number and percentage of maternal subjects with each pregnancy outcome will be tabulated with its exact 95% CI by group.
 
By subject listings of adverse pregnancy outcomes will be prepared but will not be released until the final, unblinded analysis has been completed.

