Infant subjects	
From birth through 6 months (Visit 4-NB) after birth, occurrences of SAEs, AEs leading to study withdrawal, and medically attended AEs
 
From birth through 1 year (Visit 5-NB) after birth, occurrences of SAEs, AEs leading to study withdrawal, and MAEs
	
For each category:
 
 - SAE, - MAEs 
The number and proportion of infant subjects who experienced at least one event from birth up to 6 months after birth and the number and proportion of infant subjects who experienced at least one event from birth up to 1 year after birth will be tabulated with 95% CI by group.
 
By-subject listings of SAEs, AEs leading to study withdrawal and MAEs will be prepared.

	
From birth to 6 months after birth (Visit 4-NB), occurrences of RSV-associated LRTI(s), Severe LRTI(s), very severe LRTIs and RSV-associated hospitalizations (according to the case definitions in Section 4.2.6 in the protocol)
	
For each category:
 
 - RSV-associated LRTI, - Severe LRTI, - Very severe LRTI - RSV-associated hospitalization 
The number and proportion (with 95% CI) of subjects with at least one event will be calculated and tabulated by group.

CONFIDENTIAL209544 (RSV MAT-004)
Statistical Analysis Plan Amendment 3**5.3.2. Additional considerations****5.3.2.1. Analysis of solicited events**

The analysis of solicited events will be performed on Solicited Safety Set. The intensity of the following solicited events will be assessed as described:

Table 7 Intensity scales for solicited symptoms in adults

Adults/Child (≥6 years)		
Adverse Event	Intensity grade	Parameter
Pain at injection site	0	None
	1	Mild: Any pain neither interfering with nor preventing normal every day activities.
	2	Moderate: Painful when limb is moved and interferes with every day activities.
	3	Severe: Significant pain at rest. Prevents normal every day activities.
Redness at injection site		Record greatest surface diameter in mm
Swelling at injection site		Record greatest surface diameter in mm
Temperature		Record temperature in °C/°F (with 1 decimal) Temperature will be analysed in 0.5°C increments from ≥ 38.0°C /100.4°F) Grade 3 fever is defined as > 39.0°C /102.2°F
Headache		
Fatigue	0	Normal
Nausea	1	Mild: Easily tolerated
Vomiting	2	Moderate: Interferes with normal activity
Diarrhea	3	Severe: Prevents normal activity
Abdominal pain		

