10.2. TFL TOC

The Table Figure Listing (TFL) Table Of Content (TOC) which itemizes the planned list of TFL and their associated lay-out is developed as a separate document. Please note the protocol of this study was developed based on V17 template and the term ‘solicited administration site event’ and ‘solicited systemic event’ are used, however, at the development of the TFL TOC, only V16 standard catalog is available and still ‘solicited local adverse event’ and ‘solicited general adverse event’ are used in the TFL mocks per this standard.

CONFIDENTIAL209544 (RSV MAT-004)
Statistical Analysis Plan Amendment 3

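### In the combined safety tables every SAE counts as systemic, so a serious injection-site reaction does not reach the administration-site rows through its SAE record

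*SAP*

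**What the plan says.** The rule is in SAP Amendment 3, section 10.1.3.10, among the sponsor's standard business rules. Its scope is limited: "For output combining solicited and unsolicited adverse events". Within that scope, "all serious adverse events will be considered general events since the administration site flag is not included in the expedited adverse event CRF pages". The absent flag is the only reason given.

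Section 5.3.1 plans combined outputs under the maternal primary safety endpoints. It asks for the number and percentage of women "with at least one administration site AE (solicited and unsolicited), with at least one systemic AE (solicited and unsolicited"), and with any AE. This is done over 7 days and again over 30 days; the latter row set ends "with any AE during the 30-day follow-up period after vaccination will be tabulated with exact 95% confidence interval (CI) by group". Both sets are repeated for Grade 3 events, related events, Grade 3 related events and medically attended events. Section 5.3.1 makes no exception for SAEs.

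Three other places bear on the reading:

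- Section 10.1.2.4 puts SAEs into the unsolicited summaries: "Unsolicited adverse event summaries are including serious adverse events unless specified otherwise".
- Section 10.2 explains the vocabulary. The protocol speaks of administration-site and systemic events, but "only V16 standard catalog is available and still ‘solicited local adverse event’ and ‘solicited general adverse event’ are used in the TFL mocks". On that reading, general means systemic and local means administration site.
- Section 5.3.2.1 keeps the solicited-only analysis separate: "The analysis of solicited events will be performed on Solicited Safety Set".

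**The concern.** The row labels in section 5.3.1 promise all administration-site events, solicited and unsolicited. The annex rule removes one class of them, the serious ones, and sends them to the systemic rows. Someone who reads the table without the annex would not know this.

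The misclassification runs in one direction. It can only lower site counts and raise systemic counts, and it falls on the most serious site reactions. The Grade 3 and Grade 3 related site rows are the most exposed, because counts there may be very small and one woman could be the whole row.

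The missing flag does not force the choice. The SAP already tabulates SAEs and unsolicited events by MedDRA preferred term, and section 5.3.2.4 already gives solicited site events terms that name the injection site. For many events the coded term would show the site without any change to the CRF.

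**Working it through.** The SAP states no figure on this point, so there is nothing to reproduce. The check has two parts: tracing the rule through the outputs, and sizing its effect.

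**1. Tracing one serious injection-site reaction through the planned outputs**

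| Output | Does the rule change it? |
|---|---|
| Administration-site row, 7 and 30 days, with Grade 3, related, Grade 3 related and medically attended repeats (5.3.1) | Yes: the SAE record is not counted |
| Systemic row, same tables | Yes: the SAE record is counted here |
| Any-AE row, same tables | No |
| Solicited events by grade (5.3.1, 5.3.2.1) | No: not a combined output |
| Unsolicited AEs within 30 days by preferred term, with Grade 3 and related repeats (5.3.1) | No |
| SAEs by preferred term, and SAE listings (5.3.1) | No |

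No section returns the event to the site row by another route.

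**2. What happens to the woman's count**

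The rows count women, not events, so the result depends on what else she reported. *Qualifying* means meeting the criterion of the row in question, for example Grade 3 and related.

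| Another qualifying site event? | Another qualifying systemic event? | Site row | Systemic row |
|---|---|---|---|
| No | No | −1 | +1 |
| No | Yes | −1 | 0 |
| Yes | No | 0 | +1 |
| Yes | Yes | 0 | 0 |

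One event therefore moves each row by at most one woman.

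**3. Size of one woman**

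Inputs: 213 vaccinated (SAP Amendment 2, document history); three groups at 1:1:1, up to 100 per group (section 3); exact Clopper-Pearson limits (section 10.1.5.1). The even split is an assumption: 213/3 = 71.

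- At 71 per group: 1/71 = 1.4%. 
- At 100 per group: 1/100 = 1.0%.

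Take a group in which one woman has a site event of the kind tabulated, and that event is serious. With no events the upper limit is 1 − 0.025^(1/n); with one event the limits are the usual beta quantiles.

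| n | Site row under the rule | Site row if classed by site |
|---|---|---|
| 71 | 0/71 = 0% (95% CI 0 to 5.06%) | 1/71 = 1.41% (0.04 to 7.60%) |
| 100 | 0/100 = 0% (0 to 3.62%) | 1/100 = 1.00% (0.03 to 5.45%) |

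**4. How likely it is to arise**

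The SAP gives no rate for serious site reactions, so the rates p below are assumptions. The chance of at least one in a group of n is 1 − (1 − p)^n.

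| Assumed p | n = 71 | n = 100 |
|---|---|---|
| 0.1% | 6.9% | 9.5% |
| 0.5% | 29.9% | 39.4% |
| 1% | 51.0% | 63.4% |
| 2% | 76.2% | 86.7% |

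These are chances that a serious site reaction occurs. The chance that a site row changes is lower, because some of these women will have another qualifying site event.

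**The case against.** The strongest reply is that this is a disclosed convention. It is written down in advance, limited in scope, explained by the CRF design and contradicted by nothing else in the SAP. That stands: the rule is deliberate. But a rule fixed in advance can still give a wrong classification, and this one does whenever a serious site reaction occurs.

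The second reply is that nothing is lost from the report. A reader might infer that the rule hides the worst local reactions. The document does not support that. Maternal SAEs are "tabulated by group and by Medical Dictionary for Regulatory Activities (MedDRA) preferred term" and listed by subject, unsolicited events are shown by preferred term with Grade 3 and related repeats, and the any-AE row is unchanged. What is affected is one site/systemic split.

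The third reply concerns size. A reader might take it that every such event moves 1.4 points out of the site row and 1.4 points into the systemic row. Those are upper bounds. The diary solicits pain, redness and swelling, and redness or swelling above 100 mm is scored Grade 3 (section 5.3.2.1), so a woman with a serious reaction in the first 7 days may already be in the site row, possibly at Grade 3. Likewise she may already be in the systemic row. This reply stands in full.

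The fourth reply is that MedDRA terms do not solve everything. A cellulitis or abscess reported without naming the injection site would still be classed as systemic. This also stands, and the fix has to allow for it.

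Finally, no decision rule in the SAP rests on these rows: section 5.3.1 plans counts, percentages and intervals, and the IDMC has its own SAP. That limits the importance of the point but does not make the label correct.

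**Conclusion.** The point holds and is minor. Under section 10.1.3.10 a serious injection-site reaction is not counted through its SAE record in the administration-site rows of the primary safety tables, and it is counted in the systemic rows. The effect is at most one woman per event in each row: 1.4 points at 71 per group or 1.0 point at 100. It is nil in the site row when she has another qualifying site event, nil in the systemic row when she has another qualifying systemic event, and nil throughout if no serious site reaction occurs.

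The conclusion rests on reading general as systemic, which section 10.2 supports. The 1.4-point figure also rests on an even split of the 213 women vaccinated. How often the case arises cannot be judged from the SAP.

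**What to change.** Replace the rule in section 10.1.3.10 with wording such as: in combined outputs an SAE is classed as an administration-site event when its MedDRA term denotes an injection-site or vaccination-site reaction, and otherwise as systemic; SAEs whose coded term does not name the site are reviewed blinded to treatment group and classed before unblinding. Fix the term list before unblinding as well. It must go beyond the pain, redness and swelling terms of section 5.3.2.4, which cover only solicited events.

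Add a footnote to the combined tables stating the rule used. If the sponsor keeps the present rule, the footnote is the minimum: it should say that SAEs are counted only as systemic.

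The cost is a sentence or two of SAP text, a short term lookup, a blinded review of what should be few records, and a small departure from the sponsor's standard business rule. No CRF change is needed.

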10.1.4. Display of decimals**10.1.4.1. Percentages**

Percentages and their corresponding confidence limits will be displayed with:

- no decimals when there are fewer than 50 subjects in each tabulated group
- one decimal when there are at least 50 subjects in at least one tabulated group

Exceptions will be made for percentages that are not 0% or 100% but appear as 0% or 100% due to rounding. For these specific cases the number of decimals will be increased until the displayed value is no longer 0% or 100%. Examples are given in the following table.

n/N	Displayed percentage
10/45	22%
1/45	2%
10/55	18.2%
1/55	1.8%
1/300	0.3%
1/3000	0.03%
1/30000	0.003%
299/300	99.7%
2999/3000	99.97%
29999/30000	99.997%

- The display of additional decimals for values close to 0% or 100% will be applied only to point estimates and not confidence limits, which can be rounded and displayed as 0% or 100%.
- Values of exactly 0% or 100% will be presented with no decimals regardless of the number of subjects per tabulated group.

10.1.4.2. Demographic/baseline characteristics statistics

The mean, median, and standard deviation for continuous baseline characteristics (height, weight, body mass index (BMI), pre-vaccination body temperature) will be presented with one decimal.

CONFIDENTIAL209544 (RSV MAT-004)
Statistical Analysis Plan Amendment 3

The minimum and maximum values and quartile values (if required) will be presented with the same number of decimals as the observed values.

The maxima and minima of transformed height variables will be displayed with no decimals.

The maxima and minima of transformed weight variables will be displayed with no decimals with the exception of values are below 10kg where one decimal will be displayed.

The maximum and minima of transformed body temperatures will be displayed with one decimal.

10.1.4.3. Serological summary statistics

The number of decimals used when displaying geometric mean titers (GMT) or concentrations (GMC) and their confidence limits is shown in the following table:

GMT or GMC value	Number of decimals to display
<0.1	3
>=0.1 and <10	2
>=10 and <1000	1
>=1000	0

When multiple categories of GMT or GMC values are present in the same table, the number of decimals displayed should match that of the smallest category (i.e. the one with the higher number of decimals). For example, if GMT or GMC values of <0.1 appear in the same table as values of >=0.1 and <10, 3 decimals should be displayed for both.

GMT or GMC ratios and their confidence limits will be displayed with 2 decimals regardless of the actual values.

10.1.5. Statistical methodology**10.1.5.1. Exact confidence intervals around proportions**

The exact confidence intervals around within-group proportions are derived using the method of Clopper and Pearson. [[Clopper](#), 1934]

